### 8.3 Reporting of Safety Issues

In the event of an AE/SAE, the Investigator will immediately initiate appropriate therapy and management according to her/his medical judgment and will decide whether to withdraw the subject from the study.

The subject must be followed up by additional examinations according to the medical judgment of the Investigator, until the AE/SAE and/or abnormal condition is resolved or the Investigator deems further observations or examinations are no longer medically indicated.

#### 8.3.1 Safety Data Notification, Reporting, and Monitoring

##### 8.3.1.1 *Reporting of Adverse Events (AEs)*

All AEs will be recorded on the appropriate and corresponding AE Form of the CRF by the Investigator. All AEs must be reported whether or not considered causally related to IMP. For every AE, the Investigator will provide an assessment of the severity and causal relationship to

## ALLOB-DU1 - Clinical Study Protocol

ALLOB-DU1_CSP	V 05	Author: [name]	February 02, 2017	Pg. 84/136
---------------	------	-------------	-------------------	------------

the IMP and document all actions taken with regard to the IMP, and any other treatment modalities for the AE. Treatment of any adverse event is at the sole discretion of the Investigator and according to current good medical practice. Any medication administered for the treatment of an AE should be recorded in the patient's CRF.

If the outcome of an AE is not available at the time of the initial report or at study exit (premature or not), follow-up will proceed until outcome is known. All collected data will be recorded in source documents.

#### 8.3.1.2 *Notification and reporting of Serious Adverse Events (SAEs)*

##### *Expedited Reports – Individual Case Safety Reports*

In the event of any SAE related or not to trial procedure or treatment and/or any other event or relevant information which require a re-evaluation of the benefit-risk ratio, occurring from Screening Visit up to the end of the post-study open follow-up period (24 months after the end of the study), the Principal Investigator will within 24 hours of event occurrence or awareness:

1. Notify the Study Safety Officer (SSO) by phone: Safety Events Phone Number, 24/7 cover: [REDACTED]
2. Record it on the corresponding CRF Form (SAE form) and send it by fax [REDACTED] [REDACTED] or per email [REDACTED] to the SSO who will immediately inform the Sponsor of the safety event occurrence

The CRF will be completed (by the PI) thereafter as soon as possible.

Briefly, the SAE Form (and the related Follow-up Forms if needed) will include the following information and differentiated assessment:

- Subject identification: Patient Identification Number, age, and sex
- SAE diagnosis and description, start and end dates, concomitant drugs and history
- Outcome (recovery with or without sequelae, unchanged, improvement, worsening, death, or other) and action(s) taken (none, subject discontinuation and withdrawal from the study, change in concomitant medication(s) and/or new medication(s), other treatment(s) and/or therapeutic procedure(s) i.e., invasive procedures, surgery, or unknown)

## ALLOB-DU1 - Clinical Study Protocol

ALLOB-DU1_CSP	V 05	Author: [name]	February 02, 2017	Pg. 85/136
---------------	------	-------------	-------------------	------------

- Criteria for seriousness (death, life-threatening, persistent or significant disability or incapacity, new or prolonged hospitalization, congenital abnormality or birth defect, important medical event), severity (mild, moderate, severe), and frequency (intermittent, continuous, or other)
- Causal relationship with the IMP (assessment of drug-event causal relationship and consistency with applicable product information, e.g., the Investigator's Brochure and evaluated as certain, likely, unlikely, unrelated, unknown or inassessable)
- Causal relationship with the trial procedures, including blood sampling and the product implantation (implantation , surgery, anaesthesia)
- Relationship with the study disease and/or underlying, concomitant, and/or intercurrent diseases, relationship with concomitant medication or treatment, and/or drug interactions
- Any other relevant information

Based on data and information available in both the SAE Form and in the Investigation and Conclusion Report (see below) (and additional queries, if needed), the SSO will notify the occurrence of SUSAR, SAR, and/or SAE related to the trial procedures to both Eudravigilance database and ECs (all Member States concerned), and to all concerned PIs and Sponsor in agreement with all applicable national legislation.

This notification will be sent by the SSO to the ECs and Eudravigilance database, while blinding will be preserved for both the PIs and Sponsor.

SUSARs that are fatal or life-threatening are recorded and reported within 7 days of awareness. Other SUSARs are recorded and reported within 15 days of awareness.

#### 8.3.1.3 *Notification and Reporting of Serious Adverse Reaction related to the Human Biological Material*

In the case a reported SAE (including SUSAR and SAR) is identified by the Sponsor as being potentially related to the use of human biological material for the manufacturing of ALLOB®, the Managing Physician (MP) of the Intermediary Structure will be immediately informed. The Managing Physician will initially report this SAE potentially related to the use of Human

## ALLOB-DU1 - Clinical Study Protocol

ALLOB-DU1_CSP	V 05	Author: [name]	February 02, 2017	Pg. 86/136
---------------	------	-------------	-------------------	------------

Biological Material to the Belgian CA (Biovigilance) and the Tissue Bank with 24 hours of the event occurrence or awareness in line with the Belgian law of the December 19, 2008 on the used human biological material and applicable Royal Decree.

Then, based on the information available in the CRF SAE Form, the Managing Physician will start on investigating to confirm if the safety event is related to the procurement, collection, testing, processing, storage, labelling and packaging, delivery, transport, and/or distribution of the tissues and cells, and/or to the quality and safety of the Biological Material. The Investigation and Conclusion Report have to be submitted to the Belgium CA of Biovigilance and the Tissue Bank within 5 days of awareness by the MP. In parallel, investigating conclusion reports are communicated by the MP to the SSO (who will notify Investigator, CRA, and Sponsor) and if applicable complete the information that has been communicated via the Eudravigilance system.

If a serious safety issue is identified, either upon receipt of an individual case report or upon review of aggregate data, the Sponsor will issue a communication to all Principal Investigators as soon as possible. A safety issue that impacts upon the course of the trial, including suspension of the trial, safety-related amendments to the Study Protocol, change or update of Subject Information Sheet and Informed Consent Form or Investigator's Brochure, will also be reported to the Principal Investigators (after prior submission and approval by the CAs and ECs).

#### **8.3.2    Annual Safety Reports – Development Safety Update reports (DSURs)**

In addition to the expedited reporting, the SSO will provide annual development safety update reports (DSUR) to CAs, ECs, and Sponsor, including all SUSARs, SARs, and/or SAEs related to the trial procedures, together with an overview of all other SAEs, AEs, and SAR that have occurred during the reporting period (in all sites and countries).

The DSUR should be submitted no later than 60 calendar days from the DSUR data lock point; based on the date of the Sponsor's first authorisation to conduct the clinical study in any country in line with the ICH Topic E2 F.

### 8.3.3 Safety Data Monitoring

The occurrence of AEs, SAEs, and SAR will be monitored during the whole study period on an on-going basis by the Study Safety Officer, the Managing Physician of the Intermediary Structure, and the Sponsor. The Sponsor will also receive from the Study Safety Officer a regular detailed updated listing of all AEs, SAEs, and SAR.

### 8.3.4 Data Safety Monitoring Board

A Data Safety Monitoring Board (DSMB) will be established to assess the safety data and the efficacy endpoints when 6-month post treatment results for the first 16 assessable patients are available. The safety and efficacy data of the supplementary patients enrolled after the first 16 treated patients will be also analysed.

This board will recommend to the Sponsor whether to continue, modify or stop the trial based on:

- the efficacy data of the first 16 assessable patients (primary endpoints at Month 6)
- all the available safety data of all the treated patients.

A guidance document (DSMB chart) will be established to ensure proper monitoring of the data.

## 8.4 Management of Safety Issue

### 8.4.1 Procedure in case of Pregnancy

Women included in the study must be post-menopausal (defined as at least 12 months post cessation of menses), surgically sterile or, for women with childbearing potential, using a reliable method of contraception for at least 6 weeks prior to study entry (Visit #1) and during the whole study period. Women with childbearing potential will further undergo a pregnancy test at all study visits, and at the last visit to the clinic in case of premature discontinuation.

If a female patient becomes pregnant during the trial, after the treatment with ALLOB®, the patient must immediately inform the investigator. These patients will not be excluded and will

## ALLOB-DU1 - Clinical Study Protocol

ALLOB-DU1_CSP	V 05	Author: [name]	February 02, 2017	Pg. 88/136
---------------	------	-------------	-------------------	------------

be followed-up as foreseen by the Clinical Study Protocol for safety, clinical and laboratory parameters but not for radiological examinations (Chest X-Ray, CT-scan and X-ray of the fracture).

Any pregnancy will be handled as an SAE regardless the relationship between the IMP and the event. Any complication arising during pregnancy will be recorded as an AE and will constitute a SAE if it fulfils any of the specified criteria for a SAE.

At the end of the pregnancy, whether that is full-term or premature, information on the status of the mother and child will be forwarded to Study Safety Officer.

If the outcome of pregnancy is:

- Elective abortions without complications, they will be recorded, documented and reported to the Study Safety Officer and CRO, but they should not be handled as AEs;
- Any spontaneous miscarriages or abortions for medical reasons, or congenital abnormalities or birth defects, will be recorded, documented, reported, and handled as SAEs and full details will be requested.

#### 8.4.2 Emergency Procedures

In case of SAE or any other safety event or medical concern, the following contact will be available (24/7 cover) for continuous support and assistance (Study Safety Officer):

*Emergency and Safety Events Phone Number:* [REDACTED]

The Investigator is responsible for ensuring that procedures and expertise are available to cope with medical emergencies during the study. Each patient will receive a Patient Study Card with the name and surname and the Patient Identification Number, Title and EudraCT Number of the study, type of treatment received (Advanced Therapy Medicinal Product (cell product), and Name of the Sponsor. This card will also record the name, surname, full address, and phone number of the Investigator, the address and phone number of the Emergency Room of the Investigating Site, and the Emergency and Safety Events Phone Number (24/7 cover). The aim of this card is to inform any physician having to deal with a patient in an emergency situation

**ALLOB-DU1 - Clinical Study Protocol**

ALLOB-DU1\_CSP | V 05 | Author: [name] | February 02, 2017 | Pg. 89/136

that the patient is in a clinical trial and that he/she can contact the trial Investigator for more relevant information. Patients will be instructed to carry this card around at any time during the study.

For any other questions or study information, the following contact will be available (office hours 08:00 to 17:00) for continuous support and assistance:

*Hotline - Phone Number:* [REDACTED]

*Hotline - E-mail:* [REDACTED]

### **8.5 Long-Term Pharmacovigilance System**

Finally, during the course of the trial, the Sponsor plans to design, develop, and submit to the relevant CAs, a detailed strategy for long-term patient follow-up, under Pharmacovigilance Plan in line with the ICH Topic E2 E.

## ALLOB-DU1 - Clinical Study Protocol

ALLOB-DU1\_CSP

V 05

Author: [name]

February 02, 2017

Pg. 90/136

## 9 PREMATURE REMOVAL FROM THE STUDY

### 9.1 Reasons for Early Discontinuation

Notification of patient study discontinuation (and reasons for discontinuation) will be communicated to the Sponsor by the Investigator as soon as possible. The Investigator will document the circumstances for premature discontinuation in the subject's Case Report Form as follows:

- *Violation of eligibility criteria*

Patients will be withdrawn if incorrectly included (i.e., not in compliance with one or more eligibility criteria). The Investigator may contact the monitor in order to discuss the potential continuation of wrongly included patients if judged that is in the interest of the patient to continue the study.

In any case, and especially if the patient is withdrawn for safety reasons the explanation for this discontinuation due to violation of eligibility criteria should be documented in the patient's CRF.

- *Adverse Events / Serious Adverse Events*

Any patients may be withdrawn from the study at the Investigator's discretion in case of a safety concern. However, patients can be withdrawn from the study for AEs or SAEs (including notably clinical and/or laboratory events) only if the Investigator has clearly determined that the patient's withdrawal would reduce the safety risks. In this case, the CRF AE Form must be completed, explaining the rationale for withdrawal. In addition, the Investigator should ensure that adequate medical care and management will be provided to the patient.

- *Withdrawn consent*

Participation in the study is strictly voluntary. A patient has the right to withdraw from the study at any time, and for any reason, without prejudice to further treatment, care, and patient-physician relationship. Under these circumstances, an adequate standard of care will always be adopted by the Investigator. The reason(s) for withdrawing consent will also be reviewed with

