## DEFINITIONS OF TERMS

- **Adverse Drug Reaction:** any untoward and unintended responses to an investigational medicinal product related to any dose administered (having a reasonable causal relationship to the product, the term “reasonable causal relationship” meaning that there is evidence or arguments to suggest a causal relationship). Unexpected ADR is an adverse reaction whose nature, severity, specificity, or outcome is not consistent with the applicable product information (e.g., Investigator’s Brochure).
- **Adverse Event:** any untoward medical occurrence in a patient or clinical investigation subject who has been administered a pharmaceutical product and/or any investigational medicinal product and which does not necessarily have a causal relationship with this treatment. An AE can therefore be any unfavourable and unintended signs (including any abnormal laboratory findings), symptoms, or disease temporally associated with the use of a medicinal product, without any judgment about causality
- **Adverse Event of Special Consideration:** in this study, adverse event which has been identified as potentially related to allogeneic reaction
- **ALLOB®:** is a proprietary allogeneic tissue engineered product (i.e., an advanced therapy medicinal product ATMP, falling under the scope of the European Regulation 1394/2007/EC and the Directive 2001/83/EC), consisting in allogenic osteoblastic cells (ALLOB® cells), manufactured by Bone Therapeutics S.A.
- **Assessable patient:** a patient who completed all scheduled visits up to last scheduled visit (inclusive) or a patient who has been screened (V#1), treated (V#2) and who at least has completed the follow-up visit V#5 or V#6.
- **Completed patient:** a patient who completed all scheduled visits up to last scheduled visit (inclusive)
- **Contract Research Organization (CRO):** a person or an organization contracted by the Sponsor to perform one or more of the Sponsor's trial-related duties and functions
- **Discontinued or withdrawn patient** is a patient who has been enrolled, screened, randomized or treated but has withdrawn from the study before completion of the last scheduled visit

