## 9.2 Procedure for Early Discontinuation

In case of early discontinuation and whenever possible, Investigators will ask patients to perform [REDACTED] Exit Visit as the Premature Discontinuation Visit. At the end of the Exit visit, the Investigator will declare early discontinuation in the CRF. If study participation is terminated due to an AE possibly related to the study medication or trial-related procedures, the subject will however be followed by additional examinations according to the medical judgment of the Investigator until the AE is resolved or the Investigator deems further observations or examinations to be no longer medically indicated. All collected data should be recorded in the source documents and CRF.

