### 10.1 Analysis Populations

Two analysis sets will be defined:

- The safety population that will include all treated patients. (Treated patients will be defined as patients implanted with ALLOB®). As the study is not randomized and only one study group will be studied, the safety set will be used also to analyse the whole efficacy data.
- The Per-Protocol (PP) efficacy population will include all patients of the safety population without any major protocol deviation.

The definition of the populations will be finalised prior to database lock. The safety population will be considered as the primary cohort for the analysis of safety, efficacy, demographics, and baseline characteristics. Efficacy variables will be analysed using the safety population. Primary criteria and corresponding variables will be analysed in the PP population.

The patients screened will be described in the summary table presenting the disposition of patients.

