## ALLOB-DU1 - Clinical Study Protocol

ALLOB-DU1_CSP	V 05	Author: [name]	February 02, 2017	Pg. 98/136
---------------	------	-------------	-------------------	------------

- Violation of inclusion/exclusion criteria
- At least one post-inclusion protocol violation (e.g., taking of a forbidden treatment, no evaluation of major efficacy parameters)
- At least one deviation with respect to the study procedure

Frequency and percentages of patients with protocol deviations will be tabulated.

Patients presenting major deviation will be excluded from the PP population.

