## ALLOB-DU1 - Clinical Study Protocol

ALLOB-DU1\_CSP

V 05

Author: [name]

February 02, 2017

Pg. 105/136

- Missing data due to any reason other than treatment-related AE leading to study withdrawal will be imputed using last observation carried forward (LOCF) from previous visit (scheduled or unscheduled visit).
- Missing values in-between two measured values will be extrapolated using linear mixed models.

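### Section 9.1 withdraws ineligible patients by default, even after the single implantation, so observed Month 6 data may be replaced by LOCF in an all-treated primary set

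*Combined protocol and SAP*

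**What the plan says.** Section 9.1 lists violation of eligibility criteria as a reason for early discontinuation: "Patients will be withdrawn if incorrectly included (i.e., not in compliance with one or more eligibility criteria". One exception follows: "The Investigator may contact the monitor in order to discuss the potential continuation of wrongly included patients", if continuing is judged to be in the patient's interest.

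The Definitions of Terms describe a discontinued or withdrawn patient as "a patient who has been enrolled, screened, randomized or treated but has withdrawn from the study before completion of the last scheduled visit", so the term reaches patients already implanted.

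Section 10.1 defines "The safety population that will include all treated patients" and adds that "the safety set will be used also to analyse the whole efficacy data". Section 10.5.3 lists violation of inclusion or exclusion criteria among the protocol deviations and states: "Patients presenting major deviation will be excluded from the PP population". Section 9.3 rules out replacement of withdrawn patients.

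On missing efficacy data, section 10.8 uses the worst observation when withdrawal follows a treatment-related adverse event. Missing data from any other cause "will be imputed using last observation carried forward (LOCF) from previous visit", scheduled or unscheduled.

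Section 9.2 begins "In case of early discontinuation and whenever possible, Investigators will ask patients to perform" and goes on to an exit visit; part of that sentence is blacked out.

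**The concern.** ALLOB is given once. After implantation, withdrawing a patient for an entry violation cannot reduce exposure; it can only stop the planned assessments. The primary analysis still counts that patient, so the plan creates a missing outcome that it then has to impute. The per-protocol set already exists to show what happens when eligibility violators are left out.

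The exception in section 9.1 raises a second issue. Whether a treated, ineligible patient stays is decided individually and after the fact, in an open single-arm study where the investigator may already know how the fracture is doing. That discretion can select which outcomes are observed and which are imputed.

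At stake are the completeness of the primary endpoint in a set of at most 32 patients, the make-up of the 16-patient interim set, and scheduled safety data at 6 months for an allogeneic cell product.

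**Working it through.** **1. Is there a figure in the plan to reproduce?** Not on this point: the protocol gives no expected number of eligibility violations. The nearest figure is the 10% non-assessable allowance in section 10.7. 32 / 0.9 = 35.6, which rounds up to 36 against the stated 35; conversely 35 × 0.9 = 31.5. The difference is rounding, and the allowance does not say how many patients would be eligibility withdrawals.

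**2. Who is caught?** Section 9.1 has no condition on implantation, and the definition of a withdrawn patient includes treated patients. A treated patient found ineligible therefore falls under the default rule and also stays in the safety population of section 10.1.

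**3. What happens to the outcome?** Failure at Month 6 (sections 2.2.2, 10.2 and 10.5.6.1) means rescue surgery, or both a patient-rated global disease evaluation that has not improved by 25% and a TUS that has not risen by 2 points.
- Scores: LOCF applies. If only baseline values exist, change is zero on both and the patient is a failure by construction. If an early global score happened to be 25% better, the patient is a success on the literal wording, with no later CT needed. The direction of error is not fixed.
- Rescue surgery: sections 3.2.3 and 5.6 place it from Month 3. For a patient withdrawn before then, this component would largely go unseen.

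**4. What do the safeguards deliver?**
- Exit visit (9.2): requested when possible, at the time of withdrawal, not at Month 6.
- Additional examinations after withdrawal (9.2): promised when participation ended because of a possibly related adverse event.
- Adverse events open at exit (8.3.1.1): followed until the outcome is known. This covers existing events, not new ones.
- SAE notification (8.3.1.2): runs to 24 months after the end of the study, without saying whether withdrawn patients are included.
- Thorax X-ray and liver ultrasound for ectopic mineralization (7.2.2): set at 6 months, so an earlier exit visit cannot stand in for them.

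**5. Weight in the final analysis.** Let k be the number of treated patients withdrawn for ineligibility. The protocol does not give k; 1 to 3 is an assumption. The share of the success rate resting on imputation is k / 32:
- k = 1: 1/32 = 3.1 points
- k = 2: 2/32 = 6.3 points
- k = 3: 3/32 = 9.4 points

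**6. Weight at the interim.** The interim uses the first 16 assessable patients, with an efficacy limit of 12 or more successes (2.5 and 10.5.8.3). Assessable requires Visit #5 or #6 (Definitions of Terms). There are two cases.
- Withdrawn before Visit #5: not assessable, so outside the 16. A later assessable patient takes the place. The withdrawal decision changes who is counted but adds no imputed value.
- Withdrawn after Visit #5 and before Visit #6: counted, with a carried-forward value worth 1/16 = 6.25 points.

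For the second case the extremes can be bounded with exact binomial tails. If all k are carried forward as failures, the chance of reaching the limit at a true rate of 0.70 is P(Bin(16 − k, 0.70) ≥ 12). If all k are carried forward as successes, the chance at a true rate of 0.30 is P(Bin(16 − k, 0.30) ≥ 12 − k).

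| k | all failures, true rate 0.70 | all successes, true rate 0.30 |
|---|---|---|
| 0 | 0.450 | 0.0003 |
| 1 | 0.297 | 0.0007 |
| 2 | 0.161 | 0.0017 |
| 3 | 0.064 | 0.0040 |

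These are worst cases, and they need an entry violation to come to light in the window between Month 3 and Month 6.

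**The case against.** The strongest reply is that the protocol does not abandon these patients. Continuation is possible, an exit visit is requested, open adverse events are followed to outcome and SAE notification has a long window. LOCF keeps the patient in the denominator. Eligibility is checked over a screening period of up to 8 weeks, so the rule may mostly catch errors before implantation. Section 10.5.3 already routes major deviations to the per-protocol set. Section 8.4.1 keeps patients who become pregnant after treatment in follow-up, without radiology, which suggests an intention to retain treated patients.

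Much of this stands, and it rules out three stronger readings that a reader might infer.
- That Month 6 and safety data of these patients are lost outright. The safeguards just listed contradict that; the data may be lost.
- That the later safety course goes unobserved. The documents cannot show this, because the visit procedures, the post-study follow-up and part of the exit-visit text are blacked out. The exit visit may include the global score and a CT, so the carried-forward value need not be an early one.
- That every such patient moves the interim rate by 6.25 points. The definition of assessable excludes those withdrawn before Visit #5.

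What does not stand is that the safeguards close the gap. None of them guarantees a Month 6 global score and TUS, knowledge of rescue surgery, or the 6-month imaging. The screening and pregnancy provisions do not alter section 9.1, which has no exception for implanted patients beyond individual discussion. The protocol's own treatment of pregnancy after implantation, and its condition in section 9.1 that withdrawal for an adverse event must reduce risk, both argue for retaining treated patients by default.

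**Conclusion.** The point holds as a conflict between a default withdrawal rule and an all-treated primary set. For treated patients found ineligible, section 9.1 may replace an observed Month 6 outcome with LOCF and may cut short scheduled safety assessments, with retention decided case by case in an open study.

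The size depends on a number that the documents do not give. Under the assumption of 1 to 3 patients, 3.1 to 9.4 points of the final success rate rest on imputation. The interim effect is confined to withdrawals between Visits #5 and #6; earlier withdrawals alter the composition of the 16 instead. No sample size, type I error or power figure in the plan changes. The conclusion does not rest on the absence of anything that is blacked out. It is an avoidable source of missing data and possible selection, worth correcting, but it does not by itself undermine the design.

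**What to change.** Reconcile section 9.1 with sections 9.2, 10.1 and 10.5.3:
- Withdrawal for eligibility violation applies only before implantation.
- After implantation, the violation is recorded as a protocol deviation and affects only membership of the per-protocol set.
- Scheduled data collection continues to Month 6 and through the safety follow-up unless the patient withdraws consent.
- The protocol's existing provisions on withdrawal for safety, rescue surgery and pregnancy (including its limits on radiology) stay as they are. The change concerns data collection, not clinical management.

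The cost is about one sentence in section 9.1 with matching cross-references. It uses visits already scheduled and requires no change to the sample size or stopping limits. Any effect on site payments cannot be judged, because section 12.5 places financial terms in a separate agreement.
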